		Cycle 1					Cycle 2					End of Treatment ³²	Follow- Up (Months after EOT visit)				Survival Follow-up ³⁴	
Study Day		Day 1	Day 8	Day 15	Day 22	Day 29	Day 43	Day 57	Day 71	Day 85	Day 113						Post 6-Month Follow-up	
Cycle Day											Day 1	Day 29	Day 57	Day 85	Day 99	Every 3 Months		
Visit Window (Days)*		±1	±2	±2	±2	±4	±2	±4	±2	±2	±2	±2	±2	±2	±4	±4	±10	

21. **Registration:** Participant number and dose level allocation operated by Pfizer Inc.

22. **Investigational Product Administration:** Treatment to be administered after all other assessments required on that day have been performed.

23. **Tumor Assessments:** Tumor assessments will include all known or suspected disease sites. Screening images may be obtained within 5 weeks of registration. Imaging obtained as part of standard of care but within 28 days (-7 days) of registration may be used for screening assessment. Imaging may include chest, abdomen and pelvis CT or MRI scans, and bone scans. Bone scans will be performed at baseline if disease is suspected and on study as appropriate to follow disease. Baseline central nervous system (CNS) imaging MRI or CT Brain to be conducted only if clinically indicated based on the investigator's judgement. CT or MRI scans, as well as bone scans, when indicated, are to be done every 8 weeks (±5 days) with the first one to occur 8 weeks after C1D1 Repeat imaging will be completed every 8 weeks up to and including Month 8 (Week 32) or until disease progression that requires new treatment modality, permanent discontinuation, or death. Disease progression will be confirmed with 2 consecutive timepoints at least 4-8 weeks apart in the absence of rapid clinical deterioration. Tumor assessment should be repeated at the End of Treatment visit if more than 6 weeks have passed since the last evaluation.

CCI

25. **Acetylcholine receptor (AChR) antibody:** Sample to be sent to the central laboratory for analysis. CCI

The evaluation for AChR antibodies is included to exclude participants who test positive at screening as agreed upon with the United States Food and Drug Administration (US FDA) and to confirm requirement for evaluation if myasthenia gravis is suspected.⁹⁹

CCI

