9.4. Efficacy Analysis

In this First-In-Patient study anti-tumor activity is a secondary CCI objective. The main analysis populations will be based on mITT and EP (see Section [Analysis Sets](#)).

Disease response will be presented in the form of participant data listings that include, but are not limited to starting dose, disease response at each visit, and best overall response. In addition, progression date, death date, date of first response and last disease assessment date, and date of last contact will be listed.

Summary of objective response rates (ORR) and clinical benefit rate (CBR) will be provided by descriptive statistics.

Progression -free survival (PFS) is the time from start date to date of first documentation of progression, or death due to any cause. Progression is defined as the appearance of local, regional or distant disease of the same type after complete response or progression of pre-existing lesions. It does not include second primary malignancies of unrelated types.

Overall survival (OS) is the time from start date to date of death due to any cause.

Duration of Response (DOR) is defined as the duration of overall response measured from the time measurement criteria are met for complete response (CR) or partial response (PR) (whichever is first recorded) until the first date that recurrent or progressive disease is objectively documented (taking as reference for progressive disease the smallest measurements recorded since the treatment started).

Duration of Stable Disease (DOSD) is defined as stable disease measured from the start of the treatment until the criteria for progression are met, taking as reference the smallest measurements recorded since the treatment started, including the baseline measurements.

Clinical Benefit Rate (CBR) is defined as the proportion of participants who achieved anti-tumor responses of Complete Response (CR), Partial Response (PR), or Stable Disease for > 6 months (SD).

The Kaplan--Meier methods will be used to analyze all time to event endpoints. Details of these endpoint analyses methods will be included in the Statistical Analysis Plan.

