6. ENDPOINTS AND COVARIATES

6.1. Efficacy Endpoint(s)

CCI

The main

analysis populations will be based on mITT and EP (see Section Analysis Sets).

Disease response will be presented in the form of patient data listings that include, but are not limited to starting dose, disease response at each visit, and best overall response. In addition, progression date, death date, date of first response and last disease assessment date, and date of last contact will be listed.

Summary of objective response rates will be provided by descriptive statistics. Objective tumor response, as assessed using the Response Evaluation Criteria in Solid Tumor (RECIST) version 1.1 by calculating the Objective Response Rate (ORR) and Progression-Free Survival (PFS).

Progression-free survival (PFS) is the time from start date to date of first documentation of progression, or death due to any cause. Progression is defined as the appearance of local, regional or distant disease of the same type after complete response or progression of pre-existing lesions. It does not include second primary malignancies of unrelated types.

Overall survival (OS) is the time from start date to date of death due to any cause.

Duration of Response (DOR) is defined as the duration of overall response measured from the time measurement criteria are met for complete response (CR) or partial response (PR) (whichever is first recorded) until the first date that recurrent or progressive disease is objectively documented (taking as reference for progressive disease the smallest measurements recorded since the treatment started).

Duration of Stable Disease (DOSD) is defined as stable disease measured from the start of the treatment until the criteria for progression are met, taking as reference the smallest measurements recorded since the treatment started, including the baseline measurements.

For tumor response data, the following analyses may be performed:

1. Tumor response (CR, PR, SD, PD, etc.) by cohort and visit, separately for RECIST 1.1 and irRECIST. Investigator provided tumor response will be presented by descriptive statistics (frequency and percentage).

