2. Best overall response, by cohort, across all available tumor assessments from both treatment period and maintenance period, separately for RECIST 1.1 and irRECIST. Best overall response will be derived programmatically. In the tabular data presentation, a row of CR+PR will be added to show the results of ORR. With RECIST 1.1, tumor response (CR or PR) confirmation is optional as response rate is not the primary endpoint of the study, hence unconfirmed best overall response will be derived and presented. With irRECIST, tumor response (irCR or irPR) and disease progression (irPD) are required to be confirmed, however in this study tumor response confirmation is not required, therefore unconfirmed best overall response will be derived and presented. Descriptive statistics (frequency and percentage) will be provided.

In the “unconfirmed” analyses (ie, tumor response or progression without confirmation required), all tumor assessments data will be included for analyses. Specifically, regardless if a patient’s tumor response or progression is subsequently confirmed or not, the patient data will all be included in the “unconfirmed” analyses. This is a more comprehensive analysis where tumor confirmation is not required and not taken into account. For example in the ORR analysis, if a patient achieved CR or PR, regardless it is subsequently confirmed or not, the patient will be included in the numerator.

Additional summary combining data across different cohorts may be generated if deemed necessary. Swimmer plots will be used to display duration of treatment and tumor response at each applicable time point. Waterfall plot for individual tumor size percent change from baseline, and spider plot for individual tumor size percent change from baseline over time will be presented. These plots will be presented for RECIST 1.1 and irRECIST separately.

For all time-to-event endpoints, the Kaplan-Meier analysis may be performed if deemed necessary at the time of data analysis. If the Kaplan-Meier analysis is performed for progression-free survival, an event is defined as the first occurrence of “PD” status by investigator or death, whichever comes first, under RECIST; and is defined as the first occurrence of “irPD” status that has been subsequently confirmed or death, whichever comes first, under irRECIST. Time zero for all time-to-event analyses will be defined as the first vaccination on Cycle 1 Day 1. **CCI**

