10. APPENDIX

Appendix 1. Time to Event Data Analysis Censoring Rules

Table 3. Progression Free Survival and Duration of Response

Situation	Date of Progression/Censoring¹	Outcome
Inadequate baseline assessment	First dosing date in Cycle 1	Censored
No on-study assessments	First dosing date in Cycle 1	Censored
Alive, on treatment ² and no Progression	Date of last objective tumor assessment	Censored
Progression Documented on or between scheduled tumor assessments prior to treatment discontinuation ²	Date of first objective tumor assessment showing objective progression	Progressed (Event)
Treatment discontinuation for undocumented progression	Date of last objective tumor assessment prior to discontinuation ²	Censored
Treatment discontinuation due to toxicity or other reason	Date of last objective tumor assessment prior to discontinuation ²	Censored
Death prior to first planned tumor assessment	Date of death	Death (Event)
Death without objective progression prior to treatment discontinuation ²	Date of death	Death (Event)
Death or progression after 2 or more missed tumor assessments	Date of last objective tumor assessment prior to the event	Censored

1: For date of censorship, if a tumor assessment takes place over a number of days (eg, superficial lesions one day, scans another), the last date is used as the assessment date.

2: or within 28 days of discontinuation of treatment.

Table 4. Time to Progression

Situation	Date of Progression/Censoring¹	Outcome
Inadequate baseline assessment	First dosing date in Cycle 1	Censored
No on-study assessments	First dosing date in Cycle 1	Censored
Alive, on treatment ² and no Progression	Date of last objective tumor assessment	Censored
Progression Documented on or between scheduled tumor assessments prior to treatment discontinuation ²	Date of first objective tumor assessment showing objective progression	Progressed (Event)
Treatment discontinuation for undocumented progression	Date of last objective tumor assessment prior to discontinuation ²	Censored

Treatment discontinuation due to toxicity or other reason	Date of last objective tumor assessment prior to discontinuation ²	Censored
New anticancer treatment <28 days after discontinuation of treatment without progression	Date of last objective tumor assessment prior to new anticancer treatment	Censored
Death prior to first planned tumor assessment	Start date (C1D1)	Censored

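### SAP 6.1 gives duration of response two different starting points: the first recorded response, and the first vaccination

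*SAP*

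**What the plan says.** **Definition of DOR.** SAP 6.1 has DOR "measured from the time measurement criteria are met for complete response (CR) or partial response (PR) (whichever is first recorded", running until recurrence or progression is objectively documented. Protocol 9.4 defines it the same way.

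**Time origin for analysis.** Further on in SAP 6.1, in the paragraph on time-to-event analysis, the instruction is: "Time zero for all time-to-event analyses will be defined as the first vaccination on Cycle 1 Day 1". The visible text makes no exception for any endpoint. A redacted block follows directly.

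**Status of DOR.** The SAP's "Appendix 1. Time to Event Data Analysis Censoring Rules" contains "Table 3. Progression Free Survival and Duration of Response", and a note after Table 4 gives DOR and duration of stable disease (DOSD) the PFS censoring rules. The appendix does not restate a response-date origin for DOR.

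**Scan schedule.** Under note 23 of the Part 2 Schedule of Activities, imaging is every 8 weeks with a window of 5 days either side, "with the first one to occur 8 weeks after C1D1".

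**Kaplan-Meier.** The SAP says: "For all time-to-event endpoints, the Kaplan-Meier analysis may be performed if deemed necessary at the time of data analysis". Protocol 9.4 says: "The Kaplan--Meier methods will be used to analyze all time to event endpoints".

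**The concern.** A Cycle 1 Day 1 (C1D1) origin suits PFS and OS, which run from the start date, and DOSD, which runs from the start of treatment. It does not suit DOR. Counted from C1D1, DOR becomes time from first vaccination to progression among responders, which is PFS restricted to responders. It then includes time before the response, during which a responder is progression-free by construction.

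In the current protocol DOR is a Part 2 secondary endpoint in a single-arm cohort of about 30. There is no control arm against which a lengthened duration would stand out, and the error can only run in the favourable direction. Because the definition and the analysis instruction sit in the same section, two programmers working in good faith could produce different DOR results from the same data.

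**Working it through.** The plan states no DOR figure to reproduce, and no sample size, power or error rate depends on this point. The check is a comparison of texts followed by an identity on dates.

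**Step 1: does the general sentence reach DOR?** It covers every time-to-event analysis. Appendix 1, by its title, holds the time-to-event censoring rules, and its Table 3 names DOR beside PFS. On the SAP's own classification, DOR is included.

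**Step 2: does anything visible take DOR out again?** The definition earlier in SAP 6.1 conflicts with the sentence but does not say which prevails. The only fixed starting date named in Table 3 is the first dosing date in Cycle 1. Protocol 9.4 does not settle it either: SAP section 2 says the SAP supersedes the protocol's statistical considerations, and Protocol 9.4 refers the details of endpoint analysis to the SAP.

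**Step 3: size of the difference.** For a responder who progresses:

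- DOR as defined = progression date − date of first CR or PR
- DOR from C1D1 = progression date − C1D1 = DOR as defined + (date of first CR or PR − C1D1)

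The difference is exactly the time to first response. The same holds for responders censored without progression, with the censoring date in place of the progression date.

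**Step 4: the difference at scheduled scans** (window ±5 days; 1 month = 30.4375 days):

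| First response at | Added time | With window | Months |
|---|---|---|---|
| Week 8 | 56 days | 51–61 days | 56/30.4375 = 1.84 |
| Week 16 | 112 days | 107–117 days | 112/30.4375 = 3.68 |

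**Step 5: relative size.** The documents give no expected DOR, so 3, 6 and 12 months are assumptions chosen to show the range:

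| Assumed DOR | Analysed, response at Week 8 | Analysed, response at Week 16 |
|---|---|---|
| 3 months | 4.84 (+61%) | 6.68 (+123%) |
| 6 months | 7.84 (+31%) | 9.68 (+61%) |
| 12 months | 13.84 (+15%) | 15.68 (+31%) |

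On the scan calendar, a response at Week 8 with progression at Week 24 gives 24 − 8 = 16 weeks as defined and 24 weeks from C1D1 (+50%). A response at Week 16 with progression at Week 32 gives 16 and 32 weeks (+100%).

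**Step 6: after correction.** With DOR started at the first recorded response, the added time is zero.

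**The case against.** The strongest reply is that a specific definition ordinarily prevails over a general sentence. DOR is defined explicitly in the same SAP section and identically in the protocol, and a programmer who follows that definition gets the right answer. This stands in part. A reader might infer that the plan lengthens every DOR, but the documents do not support that, because the inflation arises only if the general sentence is allowed to override the definition. The contradiction remains either way, and the analyst should not be left to resolve it.

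Other replies, and what remains of them:

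- **Redaction.** The block after the time-zero sentence could contain an exception. That cannot be excluded. The visible sentence is complete and unqualified.
- **Scope of the SAP.** It was written for the protocol of 16 March 2018, centres on Part 1, and defers detailed Part 2 design. The Part 1 anti-tumour endpoints in Protocol 2.1 are ORR and PFS, without DOR. This reduces the present impact, but the SAP does define DOR and set its censoring, and the sentence could pass unchanged into a Part 2 update.
- **Minimum shift.** A reader might infer that each DOR would gain at least about 8 weeks. That holds for scheduled scans only. Protocol 7.4 also calls for imaging whenever progression is suspected, so a response could be recorded before Week 8.
- **Recoverability.** The SAP lists dates of first response, progression, death and last assessment, and plans swimmer plots. DOR could be recalculated from these.
- **Kaplan-Meier wording.** A reader might infer that PFS, OS or DOR results can be discarded once seen. That goes too far. Protocol section 9 lets the SAP modify planned methods, optional Kaplan-Meier is defensible for escalation cohorts of 2 to 4 evaluable patients, and the underlying dates are listed regardless. What is left is a mismatch with the current protocol that matters for Part 2.

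**Conclusion.** SAP 6.1 contradicts itself on when DOR starts. The consequence is conditional. Under the general time-zero sentence, each DOR is longer by the time to first response, about 8 weeks (51 to 61 days) for a response at the first scheduled scan and about 16 weeks at the second. Under the DOR definition there is no inflation. These sizes assume responses recorded at scheduled scans; the percentages also depend on assumed durations that the documents do not supply.

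The effect is confined to a secondary, descriptive endpoint with no visible decision rule attached. The Part 2 primary efficacy endpoint (CBR) and ORR, PFS and OS are not touched. The wording should be corrected because the fix is simple and any error would favour the regimen, but it does not threaten the trial's main conclusions. The Kaplan-Meier mismatch is a separate and weaker point.

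**What to change.** Replace the time-zero sentence in SAP 6.1 with wording such as:

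*Time zero is the date of first vaccination (C1D1) for PFS, OS, DOSD and TTP. For DOR, analysed in responders only, time zero is the date on which CR or PR (irCR or irPR under irRECIST) is first recorded.*

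Time to progression needs to be named because SAP Table 4 analyses it with a C1D1 start; listing only PFS, OS and DOSD would leave it without an origin. Carry the sentence into any Part 2 SAP update.

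In that update, also make Kaplan-Meier estimation a commitment for Part 2, to match Protocol 9.4. It can stay optional for the small Part 1 cohorts.

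The cost is a few lines of SAP text, with no new data and no change to sample size or conduct. The one visible downside is that reported DOR will be shorter than it would be if counted from C1D1.

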6.2. Safety Endpoints

The main analyses of DLTs will be based on the Per Protocol analysis set. Patients not meeting the criteria for inclusion in the Per Protocol Analysis set (ie, not evaluable for assessment of DLTs) will be replaced.

6.2.1. Analysis of Primary Endpoint

Dose Limiting Toxicity (DLT) is the primary endpoint of the study. The occurrence of DLTs observed in the dosing cohorts will govern the dose escalation as described in Section 2.1. If

a patient is withdrawn from study for any reason other than a DLT prior to completion of the 28-day safety observation period, a replacement patient will be assigned for the same dose as the replaced patient. The properties of the statistical methods for the analyses of DLTs are described in section Statistical Methods and Properties. Adverse Events constituting DLTs will be listed per dose level. Adverse Events (AEs) will be graded by the investigator according to the CTCAE version 4.03 and coded using the Medical Dictionary for Regulatory Activities (MedDRA). The focus of AE summaries will be on Treatment-Emergent Adverse Events, those with initial onset or increasing in severity after the first dose of study treatment. The number and percentage of patients who experienced any AE, SAE, treatment related AE, and treatment related SAE will be summarized according to worst toxicity grades. The summaries will present AEs both on the entire study period by dose and by cycle.

6.2.2. Adverse Events

Any events occurring following start of treatment for the first time or increasing in severity will be counted as treatment emergent. *The time period for actively eliciting and collecting AEs and SAEs (“active collection period”) for each patient begins from the time the patient provides informed consent, which is obtained before the patient’s participation in the study (ie, before undergoing any study-related procedure and/or receiving investigational product), through and including a minimum of 6 months; except as indicated below after the last administration of the investigational product.*

For patients who are screen failures, the active collection period ends when screen failure status is determined.

Events that occur in a non-treatment period (for example, washout or follow-up) will be counted as treatment emergent and attributed to the previous treatment taken.

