30. **Serious and Non-serious Adverse Event Monitoring:** Adverse events should be documented and recorded at each visit using the National Cancer Institute Common Terminology Criteria for Adverse Events (NCI CTC AE) version 5.0. Participants must be followed for AEs for 6 months after the last study treatment administration or until all drug related toxicities have resolved, whichever is later; or earlier than 6 months should the participant commence another anticancer therapy in the meantime. The time period for actively eliciting and collecting AEs and SAEs ("active collection period") for each participant begins from the time the participant provides informed consent through and including 6 months after the last study treatment administration or until all drug related toxicities have resolved, whichever is later. If the participant begins a

Protocol Activity	Screen ¹ (≤28 days)	Treatment Period										Post Treatment						
		Cycle 1					Cycle 2					End of Treatment ³²	Follow- Up (Months after EOT visit)				Survival Follow-up ³⁴	
Study Day		Day 1	Day 8	Day 15	Day 22	Day 29	Day 43	Day 57	Day 71	Day 85	Day 113							Post 6-Month Follow-up
Cycle Day											Day 1	Day 29	Day 57	Day 85	Day 99	Every 3 Months		
Visit Window (Days)*			±1	±2	±2	±2	±4	±2	±4	±2	±2	±2	±2	±2	±4	±4	±4	±10

new anticancer therapy, the period for recording non-serious AEs on the CRF ends at the time the new treatment is started. However, any SAEs occurring during the active collection period must still be reported to Pfizer Safety and recorded on the CRF, irrespective of any intervening treatment.

31. **Concomitant Treatments:** All concomitant medications and non-drug supportive interventions should be recorded in the CRF.
32. **End of Treatment Visit:** The End of treatment visit will be completed at the time point when a decision is made to discontinue study treatment. This can occur during Cycles 1 or 2 or during the Maintenance Treatment Phase of the study. Obtain these assessments if not completed in the past 2 weeks (past 6 weeks for tumor assessments).
33. **Follow up:** At least 28 days, and no more than 35 days after discontinuation of study treatment, participants will return to complete the required assessments. Participants will then return at Month 2, Month 4 and Month 6 to complete the required assessments.

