8.1.4.2. Recording Non-serious AEs and SAEs on the CRF

During the active collection period, both non-serious AEs and SAEs are recorded on the CRF.

Follow-up by the investigator may be required until the event or its sequelae resolve or stabilize at a level acceptable to the investigator, and Pfizer concurs with that assessment.

If a participant begins a new anticancer therapy, the recording period for non-serious AEs ends at the time the new treatment is started; however, SAEs must continue to be recorded on the CRF during the above-indicated active collection period.

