9.5.1. Analysis of Primary Endpoint

Dose Limiting Toxicity (DLT) is the primary endpoint of Part 1 of the study. The occurrence of DLTs observed in the dosing cohorts will govern the dose escalation as described in [Section 3.1](#). If a participant is withdrawn from study for any reason other than a DLT prior to completion of the 28-day safety observation period, a replacement participant will be assigned for the same dose as the replaced participant. The properties of the statistical methods for the analyses of DLTs are described in section [Statistical Methods and Properties](#). Adverse Events constituting DLTs will be listed per dose level. Adverse Events (AEs) will be graded by the investigator according to the CTCAE version 5.0 and coded using the Medical Dictionary for Regulatory Activities (MedDRA). The focus of AE summaries will be on Treatment Emergent-Emergent Adverse Events, those with initial onset or increasing in severity after the first dose of study treatment. The number and percentage of participants who experienced any AE, SAE, treatment related AE, and treatment related SAE will be summarized according to worst toxicity grades. The summaries will present AEs both on the entire study period by dose and by cycle.

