9.5.2. Analysis of Secondary Endpoints

Laboratory Tests Abnormalities

The number and percentage of participants who experienced laboratory test abnormalities will be summarized according to worst toxicity grade observed for each lab assay. The analyses will summarize laboratory tests both on the entire study period and by cycle (Cycle 1 and Cycles beyond 1). Shift tables will be provided to examine the distribution of laboratory toxicities.

For laboratory tests without CTCAE grade definitions, results will be categorized as normal, abnormal or not done.

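### SAEs on next-line therapy enter the all-causality treatment-emergent tables, because the window does not close at a new anticancer therapy, although recording of non-serious events does

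*SAP*

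**What the plan says.** **Collection.** Protocol section 8.1.4.2: "If a participant begins a new anticancer therapy, the recording period for non-serious AEs ends at the time the new treatment is started". For serious events the same section says "SAEs must continue to be recorded on the CRF during the above-indicated active collection period". Note 30 of the Part 2 Schedule of Activities agrees: "any SAEs occurring during the active collection period must still be reported to Pfizer Safety and recorded on the CRF, irrespective of any intervening treatment". The active collection period is a minimum of 6 months after the last dose in Protocol section 8.1.4. In note 30 it is 6 months or until related toxicity resolves, whichever comes later.

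**Classification.** Protocol section 9.5.1 describes treatment-emergent events as "those with initial onset or increasing in severity after the first dose of study treatment". SAP section 6.2.2 adds: "Events that occur in a non-treatment period (for example, washout or follow-up) will be counted as treatment emergent and attributed to the previous treatment". Neither gives a last day, and neither mentions a new anticancer therapy.

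**Tables.** Protocol section 9.5.1 plans the number and percentage of participants with any AE, any SAE, a treatment-related AE and a treatment-related SAE, by worst grade. For laboratory data, section 9.5.2 says "The analyses will summarize laboratory tests both on the entire study period and by cycle", again by worst grade. Note 33 of the Part 2 schedule says of follow-up: "Participants will then return at Month 2, Month 4 and Month 6 to complete the required assessments".

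**The concern.** The collection rule changes at the start of a new therapy, but the classification rule does not. Take a participant who stops VBIR-2, starts chemotherapy and is hospitalised with febrile neutropenia inside the collection period. The event is recorded because it is serious. It is then tabulated as treatment emergent under VBIR-2. The non-serious events of the same weeks are never recorded.

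This matters most in Part 2. AEs, characterised by frequency, severity and seriousness among other features, and laboratory abnormalities are primary endpoints there (Protocol section 2.2). There is one cohort and no comparator arm in which the same contamination would appear. Participants have already progressed on anti-PD-1/PD-L1 treatment (Protocol section 4.1.2), and study treatment runs until progression among other stopping reasons (section 3.1.2). Starting another therapy within 6 months of the last dose is therefore foreseeable.

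**Working it through.** The plan states no rate or sample-size figure for this point, so there is nothing to reproduce. The check has two parts: follow the rules as written, then illustrate the size.

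**Step 1. An event after the switch, traced through the rules**

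| Rule | Non-serious AE | SAE |
|---|---|---|
| Recorded on the CRF? (Protocol 8.1.4.2) | No | Yes, to the end of active collection |
| Treatment emergent? (Protocol 9.5.1, SAP 6.2.2) | Would be, but is absent | Yes |
| In the all-causality AE and SAE percentages? | No | Yes |
| In the treatment-related percentages? (Protocol 8.1.5, 9.5.1) | No | Only if judged related, or causality not known |
| In the DLT evaluation? (Protocol 3.2) | No | Essentially no: the window is 28 days from the first vaccination |

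Two other places bear on this. Protocol section 8.2.3 makes a fatal outcome of the malignancy within the active collection period a Grade 5 SAE, so such deaths after a switch enter the same table. SAP Appendix 1, Table 4 has a censoring rule for new anticancer treatment in time to progression; the safety section has no equivalent.

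**Step 2. Direction.** Adding participants whose only SAE occurred on next-line therapy can raise the SAE percentage and cannot lower it.

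**Step 3. Size, on assumed inputs.** From the documents: N = 30 (Protocol section 9.3, approximate). All other inputs are assumptions:

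- p0 = proportion with an SAE before any new therapy
- f = proportion who start a new therapy inside the window
- h = next-line SAE hazard per month
- m = months of overlap; in the base case this is 6 minus the gap from last dose to new therapy, so 3 to 5 months means a gap of 3 to 1 months

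With constant hazard, and next-line SAEs independent of earlier SAEs:

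- q = f × (1 − exp(−h × m))
- SAE percentage as written = 1 − (1 − p0)(1 − q)
- participants added = 30 × (1 − p0) × q

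With the window closed at new therapy, the percentage would be p0.

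| f, h, m | q | p0 = 20% | p0 = 30% | p0 = 40% |
|---|---|---|---|---|
| 0.3, 0.05, 3 | 0.042 | 23.3% (+1.0) | 32.9% (+0.9) | 42.5% (+0.8) |
| 0.5, 0.07, 4 | 0.122 | 29.8% (+2.9) | 38.5% (+2.6) | 47.3% (+2.2) |
| 0.7, 0.10, 5 | 0.275 | 42.0% (+6.6) | 49.3% (+5.8) | 56.5% (+5.0) |

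Example, bottom left: q = 0.7 × (1 − exp(−0.5)) = 0.275; 1 − 0.80 × 0.725 = 0.42; 30 × (0.42 − 0.20) = 6.6.

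**Step 4. Cross-check with simpler assumptions.** Suppose 12 to 18 of 30 switch within the window and 20% to 40% of them then have an SAE. That gives 12 × 0.20 = 2.4 to 18 × 0.40 = 7.2 participants, or 8 to 24 percentage points, before allowing for anyone who already had an SAE. If 30% already had one, independently, multiply by 0.7: 1.7 to 5.0 participants.

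**The case against.** **Treatment emergent is a timing label, not a causal claim.** This stands. A reader might infer that next-line toxicity is called caused by VBIR-2. The documents do not support that: the investigator assesses causality for every AE (Protocol section 8.1.5), and related events are summarised separately. What remains is the all-causality tables.

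**No serious-to-total ratio is planned.** This also stands. A reader might infer that a reported serious share of events is inflated, but section 9.5.1 plans percentages of participants. The affected results are the SAE percentage and the all-causality AE percentages by worst grade.

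**The SAP was written for Part 1 and the protocol dated 16 March 2018.** True, but no replacement SAP is among the documents, and the current Protocol section 9.5.1 has the same open-ended definition.

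**Sponsor reporting standards may contain a cut-off** (SAP sections 8.3, 8.3.4 and 8.3.5). They are not reproduced, so this cannot be excluded. They cannot be assumed to override the explicit sentence in SAP section 6.2.2.

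**Counting follow-up events is conservative for a regimen whose effect may be delayed.** That is a reason to keep such events visible. It does not justify mixing them with next-line events when only the serious ones are recorded. The planned by-cycle summaries also leave the Cycle 1 view largely unaffected.

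**The laboratory part is less certain.** Note 33 says only that required assessments are done, and the schedule table is too broken in the text available to say reliably which tests fall at which follow-up visit. The laboratory point is therefore limited to any follow-up samples taken after a switch.

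**Conclusion.** The concern holds for the all-causality treatment-emergent AE and SAE percentages. The rules as written put SAEs from next-line therapy into those tables without the matching non-serious events. Treatment-related summaries are affected only when the investigator judges the event related or does not know. A reader might infer that dose escalation was distorted too; the 28-day DLT window makes that very unlikely.

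On the assumed inputs, about 1 to 7 of 30 participants could be added to the SAE count. The upper figure from the simpler cross-check, 7.2, is a gross ceiling that ignores overlap with earlier SAEs. The documents give no switching or SAE rates, so the actual size is unknown. Nor do they cap SAE recording at 6 months: that is the minimum, so the overlap can be longer than illustrated.

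This should be settled before database lock. It changes how the safety profile reads, not how participants are protected.

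**What to change.** 1. In SAP section 6.2.2 and Protocol section 9.5.1, end the treatment-emergent window for the main AE and SAE tables at the earlier of the end of the active collection period and the day before the first new anticancer therapy.
2. Apply the same cut-off to the worst-grade laboratory tables, for any follow-up samples taken after the switch.
3. Present post-switch SAEs in a separate listing and count that names the new therapy, and show those judged related to VBIR-2 separately.
4. Leave SAE collection and reporting unchanged.
5. Reconcile note 30 of the Part 2 schedule. It lets AE follow-up end before 6 months when another anticancer therapy starts, yet continues SAEs irrespective of it. State the end of active collection in one way there and in Protocol section 8.1.4, since the new cut-off depends on it.

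The cost is wording, one date cut-off in programming, and one extra listing and count. The start date of the new therapy is already needed to stop non-serious AE recording. The downside is that late immune-related SAEs after a switch leave the main table; the separate count of related SAEs keeps them visible.
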